5.7.2.5. Bone Metabolism Parameters

Bone metabolism parameters including bone specific alkaline phosphatase (BSAP) and C-telopeptide of type I collagen (CTX) will be taken at Cycle 1 Day 1, Cycle 4 Day 1, and EOT visits. Descriptive statistics of observed values, absolute and percentage change from baseline values at each postbaseline visit will be presented by dose cohort.

5.7.2.6. Hemolysis Parameters

Hemolysis parameters include haptoglobin, indirect bilirubin, and lactate dehydrogenase (LDH). Haptoglobin will be taken at Screening, Day 1, 8, and 15 of Cycles 1, 2, 3, 4, 5, EOT and EOS visits. Indirect bilirubin and LDH will be taken at Screening, Day 1 and 15 of Cycle 1, Day 1 of Cycles 2, 3, 4, 5, EOT and EOS visits. Descriptive statistics of observed values, absolute and percentage change from baseline values at each postbaseline visit will be presented by dose cohort. Plots of hemolysis parameters for both mean observed values and mean percentage change from baseline over time will be presented by dose cohort and for TD and NTD separately.

5.7.3. Exploratory Endpoints

5.7.3.1. Biomarkers Related to TGF- β

For biomarkers GDF8, GDF11, and GDF15, descriptive statistics of observed values at baseline, observed values, changes and percentage changes from baseline at each postbaseline visit will be presented by dose cohort.

5.7.3.2. QoL Questionnaire

QoL questionnaires including FACT-An and SF-36 will be completed at Screening, Cycle 5 Day 1 or End of Treatment (for patients who withdraw early) visits for the Expansion Cohort only. The scoring algorithms for FACT-An and SF-36 are included in the appendix.

Individual subscale scores and total scores will be summarised by visit. All derived subscale and total scores along with all individual responses will be listed for each patient.

5.7.3.3. Other Analysis

The following additional exploratory endpoints will be presented in listings only:

- Change in spleen size by MRI (in subset of patients with no prior-splenectomy)
- Change in bone mineral density (BMD) by DXA
- Change in extramedullary hematopoiesis (EMH) mass size by MRI
- Change in leg ulcer size (area)
- Change in the 6-minute walk test (6MWT) distance in NTD patients
- Hormone parameters (including estradiol, free testosterone, and total testosterone)

For the following continuous variables, the descriptive statistics including mean, median and range will be presented by dose cohort:

- Change from pretreatment in transfusion burden in transfusion dependent patients
- Change in hemoglobin level in non-transfusion dependent patients
- Change in pre-transfusion hemoglobin levels in transfusion dependent patients

5.7.4. Subgroup Analysis

Subgroup analyses of erythroid response will be performed with the following baseline factors, for NTD and TD patients separately:

- Age (< 32 and \geq 32)
- Gender (male and female)
- Iron chelation therapy (yes and no)
- Baseline LIC (< 3, 3-5, \geq 5)
- Baseline EPO (< 200 and \geq 200), (< 200, 200-500, and \geq 500), (< 500, and \geq 500)
- Splenectomy (yes and no)

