Each TD patient in the expansion cohort had a defined "pre-transfusion hemoglobin threshold" which was calculated based on transfusion history and was used for determining when to transfuse during the study. The baseline pre transfusion hemoglobin threshold was the mean of all documented pre-transfusion hemoglobin values during the 12 weeks prior to C1D1. During treatment, if the pre-transfusion hemoglobin value was increased by \geq 1 g/dL compared to the baseline pre-transfusion hemoglobin threshold for that patient, transfusion should be delayed by a minimum of 7 days and/or the number of units transfused should be reduced by 1 or more RBC units. Patients may be transfused at the investigator's discretion for symptoms related to anemia or other requirements (e.g., infection).

Cohort ^a	ACE-536 Dose Level ^b (mg/kg)	Number of Patients
1	0.2	6
2	0.4	6
3	0.6	6
4	0.8	6
5	1.0	6
6	1.25	5
Expansion	0.8	30 ^c
Total (All Cohorts): 64		

^a Cohort escalation was based on SRT review and recommendation to enroll additional cohorts and/or the expansion cohort.

^b The ACE-536 dose level for cohort 1 was 0.2 mg/kg. The dose level indicated in the table for all subsequent cohorts was the maximum dose level that could be recommended by the SRT for escalation per the modified Fibonacci dose escalation scheme.

^c The expansion cohort consisted of 30 patients, including a minimum of 12 patients who were non-transfusion dependent and a minimum of 12 patients who were transfusion dependent (including a minimum of 6 thalassemia major patients with onset of regular transfusions before age 4 years, and a minimum of 6 patients with onset of regular transfusions after age 4 years).

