5.7.1. Primary Efficacy Endpoint

The primary efficacy endpoint is the proportion of β -thalassemia patients who have an erythroid response, defined as below:

- For non-transfusion dependent (NTD) patients, a hemoglobin increase of ≥ 1.5 g/dL from baseline sustained for ≥ 14 days (in the absence of RBC transfusions). Hemoglobin measurements within 14 days following RBC transfusion or after 56 days of last dose will be excluded from analysis.
- For transfusion dependent (TD) patients, a $\geq 20\%$ reduction in RBC transfusion burden during any rolling 12-week window on treatment compared to baseline. The rolling 12-week window starts on Day 1 and increments by 1 day, e.g., from day 1 to day 84, day 2 to day 85, day 3 to day 86, etc. The search window ends on last dose day + 56 days or last day of hemoglobin measurement, whichever is earlier.

A point estimate of the proportion of patients having a response will be presented along with its associated exact 95% confidence interval based on binomial distribution for NTD and TD patients separately.

The complete hemoglobin measurements and RBC transfusion records will be listed for each patient.

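### SAP 5.7.4 relates response to baseline EPO, LIC and age only through cut categories; a dose-adjusted continuous analysis beside the tables would recover much of the lost information

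*SAP*

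**What the plan says.** SAP 5.7.4 plans this: "Subgroup analyses of erythroid response will be performed with the following baseline factors, for NTD and TD patients separately". Three of the six factors are measured on a continuous scale:

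- Age is cut at 32.
- LIC has three bands, beginning "Baseline LIC (< 3, 3-5", with the top band starting at 5.
- EPO is grouped three ways, beginning "Baseline EPO (< 200 and": split at 200, split at 200 and 500, and split at 500.

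Sex, chelation and splenectomy are naturally two-level and are not at issue.

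Response is itself a cut of a continuous quantity. SAP 5.7.1 defines it as "For non-transfusion dependent (NTD) patients, a hemoglobin increase of" at least 1.5 g/dL, sustained for 14 days or more. For TD patients it is at least a 20% "reduction in RBC transfusion burden during any rolling 12-week window on treatment compared to baseline".

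The uncut outcomes are in the plan. SAP 5.7.3.3 lists "Change in hemoglobin level in non-transfusion dependent patients" and "Change from pretreatment in transfusion burden in transfusion dependent patients", but summarises them only by dose cohort. Protocol 11.4.2 leaves open an investigation of how biomarkers relate to response, without a method. SAP 5.2 and 5.7 say that summaries are descriptive and that no formal test is planned.

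**The concern.** The subgroup tables are the only specified analysis that shows whether baseline EPO, LIC or age goes with response. Cutting the factor treats a patient just above a threshold like one far above it. Cutting the outcome does the same to a hemoglobin rise of 1.4 g/dL against one of 1.6. Both losses fall on the same few patients, who are first divided into NTD and TD and then into two or three categories. What is at stake is exploratory: a real gradient could look like noise, and the reported rates will have wide intervals. The band edges are also ambiguous. LIC of exactly 5 fits two bands, and so does EPO of exactly 500.

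**Working it through.** **Inputs**

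- Cuts on the factors: SAP 5.7.4. Cuts on the outcome: SAP 5.7.1.
- Total size: SAP 3.1 gives "Total (All Cohorts): 64", while its cohort rows add to 6+6+6+6+6+5+30 = 65. The NTD/TD split is not given, only minimums of 12 and 12 in the expansion cohort. Assumption: 30 per stratum (64/2 = 32), with 20 to 40 shown.
- Not in the documents, so assumed: bivariate-normal predictor and outcome, correlation r of 0.3 to 0.6, overall response of 30-50%.

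**The plan's own figure.** No power or precision is stated for the subgroups. The one stated figure (SAP 3.4: n = 30, 30% against 10%, one-sided 0.05, about 87%) reproduces with a continuity-corrected normal approximation:

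(0.30 - 0.10 - 1/60 - 1.645 × √(0.1×0.9/30)) / √(0.3×0.7/30) = 0.0932/0.0837 = 1.11, which gives 86.7%.

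It concerns the overall response rate and says nothing about subgroups.

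**Information kept by one cut.** With a proportion p above the cut c, the share kept is φ(c)²/[p(1-p)].

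- p = 0.5: 0.399²/0.25 = 0.64
- p = 0.3: 0.348²/0.21 = 0.58
- p = 0.2: 0.280²/0.16 = 0.49

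**Information kept when both sides are cut** (product of the two shares)

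- Both at the median: 0.637 × 0.637 = 0.41, so 59% is lost.
- Predictor at the median, 30% response: 0.637 × 0.576 = 0.37, so 63% is lost.
- Predictor cut 20/80, 30% response: 0.490 × 0.576 = 0.28, so 72% is lost.

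These shares do not depend on n. At n = 30 they correspond to about 30 × 0.28 = 8 to 30 × 0.41 = 12 patients' worth of information.

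**Chance of detection if a two-sided 0.05 test were run.** Simulation, 10,000 runs per setting, predictor cut at the median, response 30-50%:

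| n | r | Both continuous | Both cut, chi-square | Both cut, Fisher |
|---|---|---|---|---|
| 20 | 0.5 | 64-65% | 27-32% | 17-20% |
| 30 | 0.3 | 37% | 17% | 11% |
| 30 | 0.4 | 61-62% | 28-29% | 20% |
| 30 | 0.5 | 83% | 40-44% | 31-32% |
| 30 | 0.6 | 96% | 57-62% | 47-50% |
| 40 | 0.5 | 92% | 52-57% | 43-46% |

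The continuous column uses the ordinary correlation test. A Spearman test at n = 30, r = 0.5 gives 77%, hence the range of 77-83%.

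**Which cut does the damage** (n = 30, r = 0.5). Cutting only the predictor gives 61-62%. Cutting only the outcome gives 57-62%. The two contribute about equally.

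**Sample size for 80% at r = 0.5.** Continuous, by Fisher's z: ((1.960 + 0.842)/0.549)² + 3 = 29.0, rounded up to 30. The 2×2 table needs about 70-77 by chi-square.

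**Precision of a single cell.** Five responders in 15 patients give 33%, with an exact 95% interval of 12% to 62%.

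**The case against.** The strongest reply is that power is the wrong yardstick. The SAP plans no tests, no stated objective is to find predictors, and describing the protocol-defined responder endpoint across patient groups is natural. This stands in part. The detection figures only stand in for how well an association can be seen or estimated, and the larger loss counts the outcome cut as well as the subgroup cut. It does not remove the point, because lost information blurs a descriptive estimate too.

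The assumptions are also open to challenge. The stratum size, the correlations and normality have no source in the documents. Percentage change in burden cannot fall below -100%, so normality is doubtful in TD. Fisher's test is conservative at this size, which is why chi-square is shown beside it. LIC is imaged only at selected sites (schedule of events, footnote 17), so its strata may be smaller than assumed.

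A reader might infer two stronger things that the documents do not support:

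- **That even a strong predictor would be missed.** At r = 0.6 with a median cut, the table still detects it 47-62% of the time under the same assumptions.
- **That three EPO groupings let the answer follow the data.** The groupings are nested: both two-level tables are collapses of the three-level one. All are prespecified, and no test or selection rule exists. Testing all three and keeping the smallest p-value would give a 9-11% chance of p < 0.05 under no association, but nobody plans that. What remains is that none is named as the main one.

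Finally, a plain correlation would be a poor remedy. It would pool patients assigned 0.2 to 1.25 mg/kg, and choosing among several versions of hemoglobin change or burden interval would reopen flexibility. Both objections are right, and the fix has to meet them.

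**Conclusion.** The point holds as a minor, inexpensive improvement. SAP 5.7.4 uses EPO, LIC and age only as categories against a yes/no response, and nothing in the plan uses them as continuous. Under bivariate normality the double cut loses 59-72% of the information. The claim that most is lost depends on counting both cuts, since a median cut of the predictor alone loses about 36%. At an assumed 30 per stratum and r = 0.5, detection would fall from 77-83% to 31-44% with a median cut. The direction is the same at 20 and at 40 per stratum. The actual EPO, LIC and age distributions are not in the documents, and a cut far from the median keeps less information. Nothing here touches the primary, secondary or safety conclusions.

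**What to change.** In SAP 5.7.4:

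1. Keep the category tables as descriptive display. Name the three-level EPO grouping as the main one, and make the bands non-overlapping at LIC 5 and EPO 500.
2. Add, within NTD and within TD, a regression of the continuous outcome on log EPO, log LIC and age, one factor at a time, with assigned starting dose as a covariate. Report the slope with its 95% CI and a scatter plot. A partial rank correlation adjusted for dose is an alternative. Use starting dose rather than dose received, because titration in the expansion cohort depends on hemoglobin or transfusions (Protocol 10.8.2 and 10.8.3).
3. Fix the outcome in advance. For example, use mean hemoglobin change over one named 12-week window in NTD, and percentage change in transfusion burden over the same fixed window in TD. Twelve weeks matches the baseline burden period in SAP 5.1.

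The cost is some SAP wording and a few extra exploratory outputs from data already collected. The slope assumes a roughly monotone relation, which the scatter plot lets the reader judge.

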5.8. Safety Analysis

The safety endpoints will be summarized by dose cohort using the Safety Population. The safety endpoints include the incidence of dose-limiting toxicities (DLTs), treatment emergent adverse events, changes in laboratory tests, vital signs and ECG's.

Adverse events will be coded using MedDRA Version 15.1 and above. Severity of AEs will be coded using National Cancer Institute Common Toxicity Criteria for Adverse Events version 4.0 (NCI-CTCAE v4.0).

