10.8. Patient Dose Modification and Titration

Patients in the dose escalation cohorts have a pre-determined dose level based on cohort number (see [Section 9.1](#)). Dose level titration is not allowed for patients in the dose escalation cohorts, but dose delay or reduction may be required according to Patient Dose Modification Rules ([Section 10.8.1](#)). Examples of dose level reductions for patients in dose escalation cohorts are included in [Table 2](#) below. Patients who require more than 2 dose reductions due to an AE should be discontinued from treatment and complete the end of treatment and end of study visits.

All patients in the expansion cohort will be initially treated with ACE-536 at an assigned starting dose level (to be determined) which has been deemed to be safe, well tolerated, and at least minimally effective by the SRT. Examples of possible expansion cohort starting dose levels and associated modifications (reductions and titrations) are in [Table 2](#). Rules for individual patient titrations are described in [Section 10.8.2](#) for NTD patients and [Section 10.8.3](#) for TD patients.

Table 2: Starting Dose Levels, Dose Level Reductions (All Cohorts), and Dose Level Titrations (Expansion Cohort Only)

2 nd Dose Reduction	1 st Dose Reduction	Starting Dose Level	1 st Dose Titration	2 nd Dose Titration
0.2 mg/kg	0.4 mg/kg	0.6 mg/kg	0.8 mg/kg	1.0 mg/kg
0.4 mg/kg	0.6 mg/kg	0.8 mg/kg	1.0 mg/kg	1.25 mg/kg
0.6 mg/kg	0.8 mg/kg	1.0 mg/kg	1.25 mg/kg	1.5 mg/kg
0.8 mg/kg	1.0 mg/kg	1.25 mg/kg	1.5 mg/kg	N/A
1.0 mg/kg	1.25 mg/kg	1.5 mg/kg	N/A	N/A

- Dose titration to higher dose levels is only applicable to patients in the expansion cohort.
- Expansion cohort starting dose level for TD and NTD patients to be determined by the sponsor in conjunction with the SRT (range: 0.2-1.5 mg/kg).
- Dose titration will not exceed the maximum dose level tested in the dose escalation cohorts and determined to be safe and well tolerated by the SRT.
- Patients may increase and decrease dose level per protocol as needed, however patients who require more than 2 dose reductions due to an AE should be discontinued from treatment and complete the end of treatment and end of study visits.

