10.8.2. Individual Dose Titration Rules for NTD Patients in the Expansion Cohort

For the expansion cohort, the starting dose to be administered on Cycle 1 Day 1 for NTD patients will be determined by the sponsor in conjunction with the SRT (see [Table 2](#)). For subsequent cycles, dose level may be titrated individually for each patient. For all NTD patients the dose level will be assessed for titration at C3D1, C4D1, and C5D1. The dose level should be titrated individually for each patient not to exceed the maximum dose level evaluated as follows:

- If hemoglobin increase from baseline is < 1.5 g/dL throughout the previous 2 cycles at the same dose level, the dose level will be increased by 1 dose level (unless dose modification is required).
- If hemoglobin increase from baseline is ≥ 1.5 g/dL but not sustained for at least 2 consecutive measurements during the previous 2 cycles at the same dose level, the dose level will be increased by 1 dose level (unless dose modification is required).
- If hemoglobin increase from baseline is ≥ 1.5 g/dL for at least 2 consecutive measurements during the previous 2 cycles at the same dose level, the dose level will be unchanged (unless dose modification is required).

Baseline hemoglobin to assess titration will be the average of 2 or more measurements performed during the screening period. Hemoglobin measurements within 2 weeks following RBC transfusion will be excluded from the both the calculated mean baseline hemoglobin and on study values used for evaluating dose titration for a patient.

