4. ANALYSIS POPULATIONS

For all analysis populations, patients will be analyzed according to assigned cohort.

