5. STATISTICAL METHODOLOGY

5.1. Definitions

Transfusion Dependent (TD)

Based on protocol, TD patients are defined as those who required ≥ 4 units of RBCs every 8 weeks (confirmed over 6 months prior to Cycle 1 Day 1).

For programming implementation, a patient is defined as TD if the total RBCs is ≥ 11 units during 26 weeks on or prior to Cycle 1 Day 1.

Non-Transfusion dependent (NTD)

NTD patients are those who do not meet the above definition for TD. For programming implementation, NTD patients are defined as those who received < 11 units of RBCs during 26 weeks on or prior to Cycle 1 Day 1.

Baseline Hemoglobin

Baseline hemoglobin will be an average of hemoglobin measurements within 28 days of Cycle 1 Day 1, excluding measurements within 14 days following RBC transfusion.

Baseline Transfusion Burden

Baseline transfusion burden will be calculated as the total amount of RBC transfusions during the 12 weeks on or prior to Cycle 1 day 1.

Baseline for Other Parameters

Baseline erythropoietin (EPO) is defined as the maximum test value within 28 days of Cycle 1 Day 1. For all other parameters, baseline is defined as the last observation on or prior to Cycle 1 Day 1.

Transfusion Unit Conversion

The transfusion amount measured in unit “mL” will be converted to “units” according to medical review.

End of Treatment (EOT)

Procedures and evaluations for the end of treatment visit should be performed 28 days (± 7 days) after the last dose of ACE-536.

End of Study (EOS)

Procedures and evaluations for the end of study visit should be performed 28 days (± 7 days) after the Day 113/EOT visit (56 days after the last dose of ACE-536).

Combined Dose Groups

Low dose group includes patients on 0.2mg/kg and 0.4 mg/kg dose cohorts. High dose group include patients with dose level 0.6 mg/kg and above. Suitable summaries may be presented by low/high dose as specified.

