5.8.2. Adverse Events

All AEs and SAEs occurring after the Cycle 1 Day 1 dose through 56 days after the last study drug administration are to be reported and documented on the AE CRF. All AEs collected in this study are treatment emergent adverse events (TEAE). A drug-related TEAE is defined as any TEAE related to the study medication as assessed by the investigator or with missing assessment of the causal relationship.

The following summaries will be presented by dose cohort and by low/high dose for all dosed patients as well as for NTD and TD patients separately:

- Number and percentage of patients reporting each AE, categorized by System Organ Class (SOC) and Preferred Terms (PT)
- Number and percentage of patients reporting each AE experienced by $\geq 5\%$ of patients in all patients by PT
- Number and percentage of patients reporting SAE, categorized by System Organ Class (SOC) and Preferred Terms (PT)
- Number and percentage of patients reporting Grade ≥ 3 AE, categorized by System Organ Class (SOC) and Preferred Terms (PT)
- Number and percentage of patients reporting related AE, categorized by System Organ Class (SOC) and Preferred Terms (PT)
- Number and percentage of patients reporting AE leading to drug withdrawal, categorized by System Organ Class (SOC) and Preferred Terms (PT)
- Number and percentage of patients reporting each AE categorized by SOC, preferred term, and maximum severity grade group

Note that counting will be by subject, not event, and subjects are only counted once within each SOC or preferred term. If a subject experiences the same AE at more than one severity, or with more than one relationship to study drug, the most severe rating or the stronger causal relationship to study drug will be given precedence. Any missing severity, causality, or outcome will not be imputed and classed as unknown.

All AEs will be listed. The following listings will also be provided: 1) patients with SAEs; 2) patients with Grade ≥ 3 AEs; and 3) patients with AEs leading to discontinuation

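### No planned safety table uses dose received, so the expansion column mixes 0.8, 1.0 and 1.25 mg/kg and titrated patients' safety experience at the two upper doses goes untabulated

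*SAP*

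**What the plan says.** SAP 4 sets the attribution rule: "For all analysis populations, patients will be analyzed according to assigned cohort". SAP 5.8 applies it to safety: "The safety endpoints will be summarized by dose cohort using the Safety Population". For adverse events, SAP 5.8.2 adds a second grouping ("The following summaries will be presented by dose cohort and by low/high dose for all dosed patients") and repeats the summaries for NTD and TD patients. SAP 5.1 defines the upper group: "High dose group include patients with dose level 0.6 mg/kg and above". For laboratory values, vital signs and ECG (SAP 5.8.3 to 5.8.5), only dose cohort is named.

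The cohort table in SAP 3.1 gives the expansion cohort its own row ("Expansion 0.8 30"), separate from the fixed 0.8 mg/kg cohort. Its highest escalation level is 1.25 mg/kg.

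Protocol 10.8 states that "Dose titration to higher dose levels is only applicable to patients in the expansion cohort". The Table 2 row for a 0.8 mg/kg start, from second reduction to second titration, is "0.4 mg/kg 0.6 mg/kg 0.8 mg/kg 1.0 mg/kg 1.25 mg/kg". Protocol 10.8.2 says of an NTD patient with insufficient response over two cycles at one level that "the dose level will be increased by 1 dose level (unless dose modification is required"). Protocol 10.8.3 has a parallel rule for TD patients, triggered by at least 3 units transfused over two cycles. Both are assessed at C3D1, C4D1 and C5D1.

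SAP 5.5 counts expansion patients with a dose increase and lists dosing per patient. SAP 5.9.5 makes an exposure-safety analysis optional.

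**The concern.** In an ascending-dose study the reader wants to know what happened at each dose. Here the largest cohort, 30 patients, may receive up to three dose levels, and each patient's events are shown under one column identified by the starting dose. Events that begin at 1.0 or 1.25 mg/kg cannot be told apart there from events at 0.8 mg/kg. The columns that do represent 1.0 and 1.25 mg/kg hold 6 and 5 patients.

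What is at stake is dose-level safety information, including blood pressure and hemoglobin rise, which Protocol 7.4 names as effects to watch. The count of dose increases in SAP 5.5 does not link dose to event. A reader would have to merge the dosing and adverse-event listings by hand.

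**Working it through.** The plan states no figure on this point to reproduce. The checks below use its schedule and cohort sizes.

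**Inputs.** Dosing days are 1, 22, 43, 64 and 85 (schedules of events). Adverse events are collected to 56 days after the last dose (SAP 5.8.2), so the nominal window is Day 1 to Day 85 + 56 = 141. An increase requires two previous cycles at the same level (Protocol 10.8.2 and 10.8.3). Cohort 5 (1.0 mg/kg) has 6 patients and cohort 6 (1.25 mg/kg) has 5 (SAP 3.1). The rows of that table sum to 5 × 6 + 5 + 30 = 65 against a stated total of 64, so these sizes need reconciling.

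**Step 1: permitted paths from 0.8 mg/kg.** Days run from each dose to the next change of level or to Day 141.

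| Increase at | Days at 0.8 | Days at 1.0 | Days at 1.25 | Share above 0.8 |
|---|---|---|---|---|
| None | 141 | 0 | 0 | 0% |
| C5D1 | 84 | 57 | 0 | 57/141 = 40% |
| C4D1 | 63 | 78 | 0 | 78/141 = 55% |
| C3D1 | 42 | 99 | 0 | 99/141 = 70% |
| C3D1 and C5D1 | 42 | 42 | 57 | 99/141 = 70% |

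Only the last path reaches 1.25 mg/kg, and it does so with a single dose. SAP 3.3 lets patients who roll over forgo the final visit. If the window ended at Day 113, the share would run from 29/113 = 26% to 71/113 = 63%.

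**Step 2: exposure not shown by dose.** With m patients titrated, the person-days above 0.8 mg/kg lie between 57m and 99m. The documents do not give m, so the assumed range is 0 to 30, giving 0 to 30 × 99 = 2,970 person-days. Cohorts 5 and 6 contribute 11 × 141 = 1,551 person-days with full follow-up and no reductions. Titrated exposure would exceed that at 16 patients if all were raised at C3D1 (16 × 99 = 1,584), or at 28 if all were raised at C5D1 (28 × 57 = 1,596).

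**Step 3: what the fixed-dose columns can say.** With zero events in n patients, the exact 95% upper limit is 1 − 0.025^(1/n): 45.9% for n = 6, 52.2% for n = 5, and 28.5% for the two pooled (n = 11).

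**Step 4: direction.** Assume 2 of the 11 fixed-dose patients have an event (18.2%) and 10 titrated patients are added:

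- titrated rate 0%: 2/21 = 9.5%
- 10%: 3/21 = 14.3%
- 20%: 4/21 = 19.0%
- 30%: 5/21 = 23.8%
- 50%: 7/21 = 33.3%

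The rate can fall or rise.

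**Step 5: the other groupings.** Every step from 0.8 mg/kg upward stays in the high group, so the low/high table neither misplaces a patient titrated up nor separates the doses. The dose-limiting toxicity window closes 28 days after the first dose and the first possible increase is on Day 43, so those rates do not change.

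**The case against.** The strongest defence is that the expansion column answers a legitimate question. It describes a regimen that starts at 0.8 mg/kg and is titrated, which is the individualised dosing that Protocol 9.2 sets out, and it is not merged with the fixed 0.8 mg/kg cohort. That stands, provided the column is labelled so. It is also true that all summaries are descriptive, that all events and doses are listed, and that the safety review team monitors the expansion cohort. None of these produces a table by dose received.

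A reader might infer that the plan makes 1.0 and 1.25 mg/kg look safer than they are. The documents do not support this. Escalation patients cannot be titrated upward, so cohorts 5 and 6 keep their own numerators and denominators. Leaving titrated patients out removes events and patients at risk together. Those patients are also selected for insufficient response after at least two cycles, and Step 4 shows that the rate could move either way.

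A reader might also take the planning response rate of 30% to imply that 70% of the expansion cohort, 21 patients, would be titrated. That does not follow. The TD trigger is an absolute unit count: a patient falling from 6 to 4.8 units per six weeks has a 20% reduction, which is a response, yet still meets the 3-unit trigger. Primary response can also first appear after C3D1.

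A fair criticism of any table by last dose is carry-over. In the phase 1 study (Protocol 7.3) the mean half-life was 15.5 to 18.5 days. On elimination alone, 0.5^(21/15.5) = 39% to 0.5^(21/18.5) = 46% of the drug remains after a 21-day interval. The last dose before onset is therefore an imperfect label, and the table must say so.

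**Conclusion.** The point holds as a gap in reporting and is worth correcting. It is not a demonstrated bias. The expansion column mixes up to three dose levels above and including the start, and no planned summary shows safety at 1.0 or 1.25 mg/kg beyond the 6 and 5 fixed-dose patients. For a patient who is titrated, 40% to 70% of the adverse-event window follows an increase above 0.8 mg/kg.

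That range assumes nominal visit days, five doses, no delays or reductions, and follow-up to Day 141. The total effect depends on the number titrated, which the documents do not give. If nobody was titrated, this gap would be empty. The describing of safety by cohort only is exact for laboratory values, vital signs and ECG; adverse events also have the low/high and NTD/TD summaries, which do not separate the doses in question.

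**What to change.** Keep every by-cohort table, and label the expansion column as starting dose 0.8 mg/kg, titrated.

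In SAP 5.8.2 add descriptive tables of all adverse events, Grade 3 or higher events, serious events and related events by the dose level most recently administered before onset. Pool escalation and expansion patients, and give patients and person-time at each level as denominators. This also places time after a dose reduction, in any cohort, at the level actually given. Do the same for blood pressure (SAP 5.8.4) and hemoglobin change (SAP 5.8.3). Reconcile the cohort sizes with the stated total first.

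Footnote three limits: a patient can appear in more than one row; dose is confounded with time on study and with insufficient response; and drug from earlier doses carries over.

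The cost is a few extra outputs from dosing and event dates already collected, with no change to study conduct. The main risk is over-reading the new rows, which the footnote addresses.
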